4.1.4 Sensitivity Analysis Population

The Sensitivity Analysis population will be defined as all subjects from the mITT population with the exclusion of subjects with protocol deviations described in the Memo to file "CRF Documentation of on-site Day 1 Visit 1 and Day 5 Visit 2 assessments done in the evening and in the morning respectively" (NTF number: 019, dated 22 Nov 2022). The algorithm for excluding subjects from this population may be expanded based on a review of analysis results and such extensions will be documented separately.

This population will be used for the sensitivity analysis of primary endpoint.

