5.1.7 Efficacy Analysis

5.1.7.1 Primary Analysis

Instantaneous pain on NRS will be summarized for actual values and change from baseline with descriptive statistics for the ITT and FAS populations by treatment group and by analysis timepoint (from Baseline to Day 5 Visit 2).

NRS-response will be defined as $\geq 30\%$ decrease from the baseline of the instantaneous pain and no rescue medication (Section 5.1.7.4.2).

CONFIDENTIAL Page 19 of 30

The number and percentage of NRS-responders at Day 5 Visit 2 will be presented descriptively by treatment groups, along with associated 95% confidence intervals.

The difference in the rate of responders at Day 5 Visit 2 will be tested between treatment groups using two-sided Fisher's exact test at the 5% error level (alpha = 0.05) and presented with its associated p-value. The null hypothesis H_0 that there is no difference in the rate of responders will be tested against the alternative hypothesis H_A that there is a difference in the rate of responders:

$$H_0: p_T - p_C = 0$$

$$H_A: p_T - p_C \neq 0$$

Where p_T denote the rate of responders at Day 5 Visit 2 in the FIRTECH Patch treatment group (treatment, T) and p_C denote the rate of responders at Day 5 Visit 2 in the No Patch treatment group (control, C). This analysis will be based on the mITT population.

A sensitivity analysis will be conducted by executing the primary endpoint analysis for subjects from the Sensitivity Analysis population. A list of subjects excluded from the Sensitivity Analysis population will be provided along with the reason for their exclusion.

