5.1.7.2.5 Adjustments for Multiple Testing

The multiplicity of key secondary endpoints will be handled using a False Discovery Rate approach (Benjamini-Hochberg) within a separate analysis table that will consist nominal and adjusted p-values. Tables with original inferential key secondary analyses will be presented with the nominal p-values.

p-values from key secondary endpoints analyses will be interpreted in a confirmatory way only in case the primary endpoint was statistically significant. Otherwise, they will be interpreted as exploratory.

CONFIDENTIAL Page 21 of 30

The final approach will be specified in the footnote of the table with multiplicity adjustment depending on the results of primary endpoint analysis.

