14.3.1.2.2	Summary of Unanticipated Adverse Device Effects by System Organ Class and Preferred Term for FIRTECH Patch Treatment Group (Safety Population)
14.3.1.2.3	Summary of Treatment-Emergent Adverse Events by System Organ Class, Preferred Term and by Severity (Safety Population)

CONFIDENTIAL Page 27 of 30

Table Number	Table Title
14.3.1.2.4	Summary of Treatment-Emergent Adverse Events by System Organ Class, Preferred Term and by
	Relationship (Safety Population)
14.3.1.2.5	Summary of Serious Treatment-Emergent Adverse Events by System Organ Class and Preferred Term
	(Safety Population)
14.3.5.1	Summary of Vital Signs (Safety Population)
14.3.5.2	Summary of Local Physical Examination (Safety Population)
14.3.6.1	Summary of Prior Medications (Safety Population)
14.3.6.2	Summary of Concomitant Medications (Safety Population)

CONFIDENTIAL Page 28 of 30

Figure Number	Figure Title
14.2.2.3.2	Other Secondary Analysis of Time Course of Pain Intensity Difference, Box Plots of Pain Intensity
	Difference (Full Analysis Set)
14.2.2.3.3	Other Secondary Analysis of Time Course of Pain Relief, Box Plots of Pain Relief (Full Analysis Set)
14.2.2.2.4	Cumulative Incidence Curve for Time (hours) to Reach Acceptable Pain (Intent-to-Treat Population)
14.2.2.3.1	Cumulative Incidence Curve for Time (hours) to Reach No Pain (Intent-to-Treat Population)

CONFIDENTIAL Page 29 of 30

Listing Number	Listing Title
16.1.7	Listing of Randomization (All Randomized Subjects)
16.2.1.1	Listing of Subject Disposition (All Subjects)
16.2.1.2	Listing of Screen Failure and Inclusion / Exclusion Criteria Assessment (All Subjects)
16.2.2	Listing of Protocol Deviations (All Subjects)
16.2.3.1	Listing of Analysis Populations (All Randomized Subjects)
16.2.3.2	Listing of Subjects Excluded from the Sensitivity Analysis Population (Modified Intent-to-Treat Population)
16.2.4.1	Listing of Subject Demographic and Baseline Characteristics (Intent-to-Treat Population)
16.2.4.2	Listing of Medical History (Intent-to-Treat Population)
16.2.4.3	Listing of Baseline Acute Low Back Pain History (Intent-to-Treat Population)
16.2.4.4.1	Listing of Prior Medications (Safety Population)
16.2.4.4.2	Listing of Concomitant Medications (Safety Population)
16.2.4.4.3	Listing of Use of Rescue Medication (Safety Population)
16.2.4.5	Listing of Non-drug Treatment/Procedure (Intent-to-Treat Population)
16.2.4.6	Listing of Medications and Non-drug Treatments/Procedures received on Day 6 (Safety Population)

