16.2.5	Listing of Patch Application (Safety Population)
16.2.6.1.1	Listing of Pain Perception (Intent-to-Treat Population)
16.2.6.1.2	Listing of Roland-Morris Disability Questionnaire (Intent-to-Treat Population)
16.2.6.1.3	Listing of Mobility Evaluation (Intent-to-Treat Population)
16.2.6.2.1	Listing of Normalized Scores (Full Analysis Set)
16.2.6.2.2	Listing of Time-to-Event Evaluations (Full Analysis Set)
16.2.6.2.3	Listing of Instantaneous Pain NRS-Response at Day 5 Visit 2 (Modified Intent-to-Treat Population)
16.2.7	Listing of Adverse Events (All Subjects)
16.2.8	Listing of Pregnancy Test Results (Intent-to-Treat Population)
16.2.9.1	Listing of Vital Signs (Safety Population)
16.2.9.2	Listing of Local Physical Examination (Safety Population)
16.2.10	Listing of eDiaries Completion and Compliance (Safety Population)

CONFIDENTIAL Page 30 of 30

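### The exclusion rule for the primary endpoint's only planned sensitivity analysis may be expanded after results are reviewed, so that supportive analysis is not pre-specified

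*SAP*

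**What the plan says.** SAP 4.1.4 builds the Sensitivity Analysis Population in two steps. The first is definite: take the mITT population and remove subjects with the protocol deviations described in note-to-file 019. The second is open: "The algorithm for excluding subjects from this population may be expanded based on a review of analysis results", and "such extensions will be documented separately".

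SAP 5.1.7.1 gives this population its single use: "A sensitivity analysis will be conducted by executing the primary endpoint analysis for subjects from the Sensitivity Analysis population". Appendix 1 lists one output for it, Table 14.2.2.2.6. No other sensitivity analysis of the primary endpoint is planned.

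The footnote to SAP Table 3 (Section 3.4) explains why the check is needed. Some on-site diary evaluations were stored as at-home entries and cannot be corrected in the data. Where a specific deviation was recorded, the SAP treats those entries as the on-site baseline or Day 5 Visit 2 value. Both values define the primary responder.

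Safeguards exist:
- SAP 5.1.7.1: "A list of subjects excluded from the Sensitivity Analysis population will be provided along with the reason for their exclusion".
- Listing 16.2.3.2: "Listing of Subjects Excluded from the Sensitivity Analysis Population (Modified Intent-to-Treat Population)".
- Listing 16.2.6.2.3: "Listing of Instantaneous Pain NRS-Response at Day 5 Visit 2 (Modified Intent-to-Treat Population)".
- Listing 16.1.7: "Listing of Randomization (All Randomized Subjects)".

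**The concern.** A sensitivity analysis is informative because its rule was chosen without knowing the answer. Here the stated trigger for changing the rule is the results themselves, not a data-quality finding or a deviation review before lock.

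The clause does not say which results are meant, who reviews them, by when, or on what criteria exclusions may be added. SAP 2.6 states that the trial is open label with no blinding procedures, and no passage requires the review to be done without treatment arm. Protocol Section 8 places SAP sign-off before database lock, but an extension documented separately is not bound by that sign-off. The SAP revision history shows this population being added in version 3.0 and modified in version 4.0, both through a versioned SAP. The clause allows a further change without one.

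At stake is the independence of the one planned check on the reclassified diary records. Exclusions added after seeing results could make agreement with the primary analysis look stronger or weaker than the 019 question alone would show. The SAP does not require the table to disclose that its population was expanded.

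**Working it through.** **Scope, from the text**

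| Element | Where | Can it change after results? |
|---|---|---|
| mITT population | SAP 4.1.2 | No expansion clause |
| Primary two-sided Fisher test, alpha 0.05, on mITT | SAP 5.1.7.1 | No |
| Confirmatory reading of key secondaries | SAP 5.1.7.2.5 | No: "p-values from key secondary endpoints analyses will be interpreted in a confirmatory way only in case the primary endpoint was statistically significant" |
| Sensitivity population and Table 14.2.2.2.6 | SAP 4.1.4, Appendix 1 | Yes |

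Only the last row is exposed.

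**Inputs for the illustration**

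SAP 2.4 gives 90 evaluable subjects per arm. The pooled two-proportion formula (two-sided 5%, 80% power) gives 81, 90, 85, 88, 84 and 82 per arm for the six rows of SAP Table 2. The largest is 90, and 180/0.90 = 200 randomized, so the plan's own figures reproduce. The actual size of the sensitivity population is not stated, so I use 90 and, as an alternative assumption, 80 per arm. All p-values are two-sided Fisher exact.

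**Step 1: how few chosen removals cross 5%**

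The starting tables below are assumed, not taken from the documents.

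- *Gaining significance.* Take 55/90 patch and 43/90 control responders, p = 0.0994. Remove three subjects, each a patch non-responder or a control responder. Removals split as patch + control give: 3+0, p = 0.0493; 2+1, p = 0.0498; 1+2, p = 0.0503; 0+3, p = 0.0507. Two of the four splits cross.
- *Losing significance.* Take 51/90 and 36/90, p = 0.0365. Remove two subjects, each a patch responder or a control non-responder: 1+1, p = 0.0509; 2+0, p = 0.0508; 0+2, p = 0.0375.

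**Step 2: how often the table would lie that close**

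For each Table 2 pair of rates, sum the product of the two arms' binomial probabilities over all outcome tables that lie within three chosen removals of the 5% line.

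| Control/patch rate | Gain, n=90 | Lose, n=90 | Total, n=90 | Total, n=80 |
|---|---|---|---|---|
| 10%/27% | 0.134 | 0.110 | 0.244 | 0.287 |
| 20%/39% | 0.128 | 0.093 | 0.221 | 0.268 |
| 30%/51% | 0.087 | 0.041 | 0.127 | 0.167 |
| 40%/61% | 0.099 | 0.041 | 0.140 | 0.159 |
| 50%/71% | 0.085 | 0.044 | 0.129 | 0.169 |
| 60%/80% | 0.110 | 0.084 | 0.194 | 0.243 |

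**Step 3: two checks on how to read this**

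- *If the observed rates equal the planned ones.* Rates × 90, rounded, give 24 vs 9, 35 vs 18, 46 vs 27, 55 vs 36, 64 vs 45 and 72 vs 54. The p-values are 0.0064, 0.0085, 0.0061, 0.0071, 0.0059 and 0.0054. Reaching p ≥ 0.05 takes at least 6, 7, 10, 12, 10 and 9 chosen removals respectively.
- *If removals are random.* Dropping five per arm at random (exact hypergeometric) crosses 5% with probability 0.078 from 55 vs 43 and 0.337 from 51 vs 36. Crossing the line is therefore not in itself a sign of selection.

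**The case against.** The strongest reply is that little depends on this table. The primary test has a fixed population, the key secondaries are gated on the primary result alone, and no success criterion is attached to the sensitivity p-value. That is right, and it limits the seriousness.

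Second, the clause permits expanding an algorithm, not picking individuals, and each exclusion needs a listed reason. Expansion can only add exclusions, so every 019 subject stays out under any version. The table would become a mixed check rather than cease to check reclassification. This also stands, and it is why the chosen-removal figures are a worst case.

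Third, the listings disclose a great deal. A holder of the full study report could rebuild the 019-only result from the listed exclusions with reasons, the mITT responder listing and the randomization listing. True, but disclosure makes an expansion visible afterwards. It does not make the analysis pre-specified.

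Fourth, the review of results may have been intended as a dry run or an arm-blind look, and the table mock-ups, which are not among the documents, may carry a footnote. Either is possible. The SAP text requires neither, and if that was the intent, saying so costs nothing.

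**Conclusion.** The concern holds as a narrow point and should be corrected. The SAP expressly allows the exclusion rule for the primary endpoint's only planned sensitivity analysis to be changed on the basis of results. No other section withdraws or limits that permission. The defect is the lack of pre-specification, and it stands without any of the arithmetic.

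The sizes are illustrative and apply to the sensitivity p-value alone. They assume 90 (or 80) per arm, true rates as in SAP Table 2 and free choice of subjects. On that basis the chance of being within three chosen removals of 5% is 13–24% at 90 per arm (8–13% could be gained, 4–11% lost) and 16–29% at 80 per arm. A clearly positive or clearly negative result would be hard to move. The primary type I error rate and the sample size are unaffected, and the documents give no sign that the clause was used.

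**What to change.** Delete the expansion sentence from SAP 4.1.4. Define the Sensitivity Analysis Population as mITT minus subjects with note-to-file 019 deviations. Freeze the subject list before database lock and before any results by arm are produced. Always report that version in Table 14.2.2.2.6. If further exclusions are examined later, label them post hoc and show them beside the pre-specified result. Keep Listings 16.2.3.2 and 16.2.6.2.3 as planned.

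The cost is one deleted sentence and one frozen list. Additional sensitivity work remains possible. The sponsor gives up only the freedom to redefine this set after seeing results.

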4.1.5 Safety Population

The Safety population will be defined as all subjects randomized into the study and, if randomized to the "patch" arm, had the device installed. This population will be used for partial demographic analysis and all safety analyses. Subjects will be analyzed according to the treatment actually received (i.e. astreated).

4.2 Treatment Groups

For summary statistics, subjects will be presented by the following treatment groups:

CONFIDENTIAL Page 16 of 30

- FIRTECH Patch all subjects randomized to Arm A: FIRTECH Infrared Therapy Patch;
- No Patch all subjects randomized to Arm B: No Patch.

For all analyses based on the Safety population, subjects will be presented by the specified treatment groups according to following:

- FIRTECH Patch all subjects received the Arm A: FIRTECH Infrared Therapy Patch;
- No Patch all randomized subjects that have not received the Arm A: FIRTECH Infrared Therapy Patch (i.e., Arm B: No Patch.).

CONFIDENTIAL Page 17 of 30

5 ANALYSIS METHODS

5.1.1 Disposition

Disposition will be summarized descriptively using counts and percentages for All Subjects by treatment group and overall. The number and percentage of subjects screened, screen failures, randomized and completed the study will be presented, together with number and percentage of subjects who prematurely discontinued from the study along with reasons for study discontinuation will be summarized.

A listing of subject's disposition status will be provided. The number of subjects in each analysis population will be summarized descriptively with counts and percentages separately. A listing of subject's inclusion to analysis sets will be provided. A subject's eligibility with inclusion/exclusion criteria completions or violations will be listed.

5.1.2 Demography and Baseline Characteristics

Demographic data and baseline characteristics will include:

- Sex;
- Childbearing Potential;
- Age (years).

Demographics and baseline characteristics will be summarized descriptively by treatment group and overall and by protocol version (< 4.0 /4.0) and overall. Summary statistics (e.g., number of subjects, mean and standard deviation, Q1, Q3, median, IQR, minimum and maximum) will be generated for all continuous variables (i.e., age) and the number and percentage of subject within each category will be presented for all categorical variables (i.e., sex and childbearing potential). The summary results will be based on the ITT population.

5.1.3 Medical History

Medical history will be coded using MedDRA (version 24.1), listed, and summarized with descriptive statistics by System Organ Class (SOC) and Preferred Term (PT) for ITT population by treatment group and overall.

5.1.4 Pregnancy and Childbearing Potential

For female subjects, pregnancy test and/or childbearing potential will be listed for ITT population.

5.1.5 Prior and Concomitant Medications

Medications will be coded with the WHO drug dictionary (WHO Drug global B3 September 2021), listed and presented by ATC Class 2 and Preferred Term (PT) for Safety population by treatment group and overall.

If a medication cannot be found in WHO dictionary, it will be coded as "WHO Code Not Defined".

CONFIDENTIAL Page 18 of 30

Private and Confidential Study No LPS16453 Date: DEC 12, 2022

Each medication will be classified as prior, concomitant or both.

Any medication taken within 4 weeks (28 days) before the first patch application (for the FIRTECH Patch treatment group) or randomization (for the No Patch treatment group) will be considered as prior.

Any medication taken on or after the first patch application (for the FIRTECH Patch treatment group) or randomization (for the No Patch treatment group) or with a start date prior to and ongoing at the time of the first patch application (for the FIRTECH Patch treatment group) or randomization (for the No Patch treatment group) will be considered as concomitant.

In case when start/stop date is incomplete, or medication is ongoing, the following assumption will be made for Prior/Concomitant classification:

- If there is reasonable possibility that medication was taken within 4 weeks (28 days) before the first patch application (for the FIRTECH Patch treatment group) or randomization (for the No Patch treatment group), the medication will be considered as prior;
- If there is no evidence that medication was taken before the first patch application (for the FIRTECH Patch treatment group) or randomization (for the No Patch treatment group), medication will not be classified as prior;
- If there is a reasonable possibility that medication was taken on or after the first patch application (for the FIRTECH Patch treatment group) or randomization (for the No Patch treatment group) and there is no evidence that medication intake was stopped prior to, then medication will be classified as concomitant.

Prior medications will be summarized and listed with ATC Class 2 and PT for Safety population by treatment group and overall.

Concomitant medications will be summarized and listed with ATC Class 2 and PT for Safety population by treatment group and overall.

5.1.6 Protocol Deviations

Protocol deviations will be listed and summarized with descriptive statistics by Deviation Type and Deviation Sub-Type for ITT population by treatment group and overall.

5.1.7 Efficacy Analysis

5.1.7.1 Primary Analysis

Instantaneous pain on NRS will be summarized for actual values and change from baseline with descriptive statistics for the ITT and FAS populations by treatment group and by analysis timepoint (from Baseline to Day 5 Visit 2).

NRS-response will be defined as $\geq 30\%$ decrease from the baseline of the instantaneous pain and no rescue medication (Section 5.1.7.4.2).

CONFIDENTIAL Page 19 of 30

The number and percentage of NRS-responders at Day 5 Visit 2 will be presented descriptively by treatment groups, along with associated 95% confidence intervals.

The difference in the rate of responders at Day 5 Visit 2 will be tested between treatment groups using two-sided Fisher's exact test at the 5% error level (alpha = 0.05) and presented with its associated p-value. The null hypothesis H_0 that there is no difference in the rate of responders will be tested against the alternative hypothesis H_A that there is a difference in the rate of responders:

$$H_0: p_T - p_C = 0$$

$$H_A: p_T - p_C \neq 0$$

Where p_T denote the rate of responders at Day 5 Visit 2 in the FIRTECH Patch treatment group (treatment, T) and p_C denote the rate of responders at Day 5 Visit 2 in the No Patch treatment group (control, C). This analysis will be based on the mITT population.

A sensitivity analysis will be conducted by executing the primary endpoint analysis for subjects from the Sensitivity Analysis population. A list of subjects excluded from the Sensitivity Analysis population will be provided along with the reason for their exclusion.

5.1.7.2 Key Secondary Analyses

Key Secondary analyses will be based on the FAS population.

5.1.7.2.1 Normalized Sum of Pain Intensity Difference

Pain Intensity Difference (PID) will be defined as instantaneous NRS change from baseline. The Sum of Pain Intensity Difference (SPID) will be calculated by multiplying the PID score at each post-baseline analysis timepoint by the duration (in hours) since the preceding timepoint. The Normalized SPID₀₋₅ will be calculated as the SPID over 5 days divided by the total duration time:

Normalized
$$SPID_{0-5} = \frac{\sum_{i=1}^{9} (T_i - T_{i-1}) * PID_i}{T_9 - T_0}$$
 ,

where $T_0 = 0$ (baseline), T_i – actual time (hours) from T_0 and PID_i – Pain Intensity Difference score at time Ti. Pain Intensity Difference, in turn, will be calculated as: $PID_i = PI_i - PI_0$, where PI_0 - Pain Intensity at time T_0 .

Normalized SPID₀₋₅ will be summarized with descriptive statistics for treatment groups and analyzed by ANCOVA model with the treatment group as fixed effect and baseline instantaneous pain NRS as a continuous covariate.

CONFIDENTIAL Page 20 of 30

5.1.7.2.2 Mobility Evaluation

Mobility evaluation (Schober's Test score and Fingertip to Floor Test score) will be summarized for actual values and change from baseline with descriptive statistics by treatment group and by visit (Baseline Visit 1, Day 5 Visit 2). Change from baseline for mobility evaluation scores will be analyzed by ANCOVA model with the treatment group as fixed effect and baseline instantaneous pain NRS as a continuous covariate.

